Statistical Considerations and Methods	
Primary Efficacy Analysis:
 
This stratified randomized double-blind phase 2b study has as its primary end-point the confirmed renal response rate after 12 months of treatment with NEOD001 or placebo and is designed to detect an absolute increase in the renal response rate of 30% (from 25% in those receiving placebo to 55% in those receiving NEOD001).
 
The primary efficacy analysis of the confirmed renal response rates after 12 months of treatment with NEOD001 or placebo will be performed with the Mantel-Haenszel (MH) test at the alpha=0.05 (two-sided) level of significance. The analysis will be stratified by the randomization stratification variables.
 
Secondary Endpoint Analyses:
 
Comparisons of mGFR and eGFR at study entry will be by the Tukey mean-difference (Bland-Altman) method determining whether the measurements are sufficiently close with alpha of 0.05.
 
Analyses of other secondary endpoints comparing patients receiving NEOD001 or placebo will depend on the endpoint. Time-to-event endpoints including time to CKD 4 or 5, to eGFR <math><</math> 15 or dialysis, to doubling of creatinine, and to <math>></math> 40% reduction in eGFR, will be analyzed by Kaplan-Meier (stratified log-rank) with alpha of 0.05.
 
The comparisons of renal response and progression in patients who have had maintained hematologic responses at 26 months will be by MH test stratified by the pre-randomization stratification factors to

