 All laboratory tests to be done locally, unless otherwise noted. When laboratory tests are obtained on the same day as NEOD001 administration they should be obtained *prior to* administration of study drug. Pregnancy tests for WOCBP as follows: **Screening:** serum test within 28 days before Month 1-Day 1; **Month 1:** serum test within 24 hours before Month 1-Day 1; **Months 2-12:** serum test preinfusion; **EOS/ETD:** serum test; **90 ( $\pm 5$ ) days after the last study drug administration:** serum test.

 Serum free light chain studies, U-PEP, U-IFE, SPEP and S-IFE will be obtained prior to administration of NEOD001 or placebo.

[figure not shown]
 Archive of baseline and confirmatory EOS visit urine samples, in consenting patients, from first morning urination will be maintained at Tufts. Samples should be obtained during the screening period before the renal biopsy. Samples will be shipped same-day overnight in kits provided. These samples will be banked for future unspecified testing.

 Renal biopsy at study entry is standard of care. Renal biopsy should be obtained after mGFR and other urine studies, including archived urine sample, have been performed. A portion of the biopsy is routinely used for frozen section and, in consenting patients, will be cryopreserved in RNA Later for future molecular testing.

 Standard-of-care follow up will include local testing every 3 months of all laboratory studies included in the confirmatory visit during the OLE study.

 Inflammatory biomarkers include IL-6, IL-8, TNF $\alpha$ , C3 and C4, CRP, SAA (A-SAA), and tryptase (at screening only). Biomarkers should be repeated if clinically indicated, i.e. the subject has a hypersensitivity reaction.

 Serum creatinine and 24 hour urine collection, including UPEP, to be sent to central lab (Covance).

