### **3.7 Definition of End of Study**

The study will end when the last subject treated with NEOD001 or placebo completes either the ETD visit or the active study period and, if eligible, the 12 months on the OLE study after the confirmatory EOS visit.

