## 4.3 Early Treatment Discontinuation

If the subject discontinues study drug prior to the initial EOS visit, the subject should return for an ETD Visit 30 ( $\pm 5$ ) days after their final administration of study drug as per Section 6.2. If a subject fails to return for the scheduled visit, a documented effort must be made to determine the reason. If the subject cannot be reached by telephone after 2 attempts, a certified letter will be sent to the subject (or the subject's legally authorized representative, if appropriate) requesting contact with the Investigator. This letter will be submitted to the IRB for review prior to use. This information will be recorded in the study records.

If the subject discontinues study drug prior to initial EOS visit, but is willing to continue to participate in study visits, continue to collect data through the ETD Visit (i.e., 30 [ $\pm 5$ ] days after their final administration of study drug). Following the ETD Visit, subsequent clinic evaluations will be standard-of-care visits with testing as clinically warranted, usually at a minimum of every 3 months. Testing in this circumstance can be performed at a distance. Every effort should be made for the subject to return to the clinic at the month 12 time point for completion of all of the initial EOS visit assessments.

Reasons for early discontinuation from study drug treatment may include, but are not limited to:

- Hematologic progression requiring immediate initiation of chemotherapy; the chemotherapy regimen should be documented on the appropriate case report form.
- Need for organ transplant or major surgery.
- Occurrence of an AE or clinically significant laboratory abnormality that, in the opinion of the Investigator, warrants the subject's permanent discontinuation from study drug treatment; the Medical Monitor ([name]) should be notified as soon as possible of any discontinuation of study drug due to an AE.
- Suspected or confirmed pregnancy or nursing during study treatment period. Female subjects whose pregnancy test is positive at the ETD visit must be followed to term or until termination of the pregnancy.

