### **6.4 Vital Status Follow-Up Phone Call**

Conduct vital status telephone call approximately 4 weeks after ETD visit or confirmatory EOS visit and approximately every 3 months thereafter until 24 months after study entry if the subject does not comply with standard-of-care visits or testing.

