### **8 STATISTICAL METHODS AND CONSIDERATIONS**

#### **8.1 Analysis Populations**

Primary efficacy analysis is based on patients who are randomized and receive treatment for 12 months with NEOD001 or placebo.

Analysis of secondary time-to-event and also safety endpoints will be based on intention-to-treat. All patients randomized and treated with NEOD001 or placebo will be included.

The following subject populations will be evaluated and used for presentation and analysis of the data:

1. The Intent-to-Treat Population will include all randomized subjects who receive any amount of study drug (NEOD001 or placebo). Treatment assignment will be based on the randomized treatment.
2. The Safety Population will include all subjects who received any amount of study drug (NEOD001 or placebo). The Safety Population will be the primary population used for safety analyses. Treatment assignment will be based on the treatment actually received. For example, in the event of randomization, dispensing, or treatment errors, subjects will be included in the treatment group based on the treatment that was received.

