### 8.3.2 Secondary Endpoint Analyses

Comparisons of mGFR and eGFR at study entry will be by the Tukey mean-difference (Bland-Altman) method determining whether the measurements are sufficiently close at alpha level of 0.05.

Analyses of time-to-event secondary endpoints comparing the NEOD001 and placebo groups will be performed by Kaplan-Meier (stratified log-rank) at an alpha level of 0.05. These endpoints include time to CKD 4 or 5, time to eGFR  $\leq$  15 or dialysis, time to doubling of serum creatinine, and time to  $\geq$  40% reduction in eGFR.

The comparisons of renal response and progression in patients with maintained hematologic responses at 26 months who received NEOD001 or placebo will be analyzed using a standard t-test and also using a Cochran Mantel-Haenszel (CMH) test stratified by the pre-randomization stratification factors. The number and percentage, with associated 95% exact confidence intervals (CI), of subjects in each category of response will be presented by treatment group. The proportional treatment difference with associated exact 95% CI will be presented.

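### The 26-month renal analysis is described as NEOD001 versus placebo, but its only fixed assessments lie in an optional, all-NEOD001 extension closed to CKD 4/5, and no rule covers patients without 26-month data

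*Combined protocol and SAP*

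**What the plan says.** **The analysis.** Section 8.3.2 specifies "The comparisons of renal response and progression in patients with maintained hematologic responses at 26 months who received NEOD001 or placebo", which "will be analyzed using a standard t-test and also using a Cochran Mantel-Haenszel (CMH) test stratified by the pre-randomization stratification factors". The synopsis names one test only: the comparison "will be by MH test stratified by the pre-randomization stratification factors". Section 2 (Objectives) lists the endpoint among comparisons of the NEOD001 and placebo groups. Section 1.1 counts the 26 months from study entry.

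**Where the data come from.** After the confirmatory end-of-study (EOS) visit, the only fixed schedule with creatinine/eGFR, 24-hour urine protein and free light chains is Table 5 in Appendix 11 (OLE). Section 3.1 makes the OLE optional and gives NEOD001 to all who enter. The Appendix 11 eligibility checklist requires completion of the active period and excludes eGFR below 30 and dialysis.

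**Outside the OLE.**
- After an early treatment discontinuation (ETD) visit, section 4.3 says "subsequent clinic evaluations will be standard-of-care visits with testing as clinically warranted, usually at a minimum of every 3 months".
- Section 4.4 treats the 12 months after the confirmatory EOS visit as part of a subject's study participation.
- Section 6.4 provides vital-status calls "until 24 months after study entry if the subject does not comply with standard-of-care visits or testing".
- Table 1, footnote 14: "Standard-of-care follow up will include local testing every 3 months of all laboratory studies included in the confirmatory visit during the OLE study".

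**Population and missing data.** Section 8.1 assigns a population to the primary analysis and states that "Analysis of secondary time-to-event and also safety endpoints will be based on intention-to-treat". It assigns none to the 26-month renal comparison. Section 8.6 covers subjects who discontinue with an ETD visit and rules out imputation.

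**The concern.** Two things go wrong if the plan is followed literally.

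**The contrast.** A placebo patient who enters the OLE can have had up to 12 NEOD001 infusions by its EOS visit. Comparing by randomised arm is still legitimate, but among OLE patients it estimates immediate versus delayed NEOD001. Neither section 8.3.2 nor section 2 says so.

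**Who is counted.** The OLE bar (eGFR below 30) overlaps with the event being counted (a 25% fall in eGFR). A patient who completed month 13, had progressed and was then barred may have no 26-month measurement. With no imputation and no carry-forward rule, that patient can leave both numerator and denominator. Two statisticians could follow this text and reach different denominators.

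At stake are the estimate and its label for one secondary endpoint.

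**Working it through.** **1. The plan's own figure.** Section 8.5 gives 41 evaluable per arm for 25% v 55%, two-sided alpha 0.05, power 0.8:

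n = [1.96·√(2·0.40·0.60) + 0.842·√(0.25·0.75 + 0.55·0.45)]² / 0.30² = 40.7, so 41 per arm; 41/(1 − 0.18) = 50.

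This reproduces (power at 41 per arm: 0.803). No size or power is given for the 26-month comparison. The 41 is used below only for scale; the maintained-response subset at 26 months would probably be smaller.

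**2. Which visit serves as month 26.** The 12th dose falls 11 × 28 = 308 days after the first. Initial EOS is near day 338 and confirmatory EOS near day 368. If the OLE starts at once, its EOS visit is near 368 + 308 + 30 = day 706. That is 25.2 28-day months from first dose, or 26.2 with 28 days of screening. The OLE EOS visit is therefore the scheduled assessment closest to month 26. Table 5, footnote 1 fits this: it sends creatinine to the central laboratory at that visit for maintained hematologic responders.

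**3. Overlap of the OLE bar with progression.** Progression is a 25% eGFR fall (section 1.1, Appendix 4). The bar is eGFR below 30. The baseline at which the two meet is 30/0.75 = 40.
- Baseline 30 to below 40: a 25% fall always lands below 30 (35 × 0.75 = 26.25), so every progressor whose fall persists is barred.
- Baseline 40 or more: reaching below 30 always takes a fall of more than 25% (from 45, more than 33.3%), so every patient barred for eGFR below 30 has progressed.
- Only baselines below 40 allow barring without progression (from 35, any fall beyond 14.3%).

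**4. Illustration of size.** The documents give no CKD 4/5 rate, so every input here is an assumption: true 26-month progression 30% (placebo) and 20% (NEOD001); c and t are the shares barred in the placebo and NEOD001 arms; q is the share of barred patients who are progressors.

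Observed difference = (0.30 − q·c)/(1 − c) − (0.20 − q·t)/(1 − t)

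| c | t | q = 1 | q = 0.75 | q = 0.5 |
|---|---|---|---|---|
| 20% | 10% | 1.4 | 4.9 | 8.3 |
| 10% | 20% | 22.2 | 18.8 | 15.3 |
| 5% | 3% | 8.8 | 9.3 | 9.9 |
| 3% | 5% | 12.0 | 11.5 | 11.0 |
| 10% | 10% | 11.1 | 11.1 | 11.1 |

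(percentage points; true difference 10)

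First row, q = 1: 0.10/0.80 − 0.10/0.90 = 0.125 − 0.111 = 0.014. Second row, q = 1: 0.20/0.90 − 0/0.80 = 0.222. On 41 per arm, 20% and 10% are about 8 and 4 patients. The table is not a bound: c = 20%, t = 3%, q = 1 gives 0.125 − 0.175 = −5.0 points, and the reverse (c = 3%, t = 20%) gives 27.8.

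**5. Power.** For 30% v 20% at 41 per arm, two-sided 0.05: Φ[(0.10·√41 − 1.96·√(2·0.25·0.75))/√(0.21 + 0.16)] = Φ(−0.92) = 0.18.

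**The case against.** **The protocol is open about the OLE, and the wording can be read as naming the original arms.** This stands in part. Several sections state that OLE patients receive NEOD001, and the past tense in section 8.3.2 does identify the original groups. There is no contradiction, but the analysis text never states what the contrast estimates by month 26.

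**Follow-up may exist outside the OLE.** This stands. A reader might infer from section 3.7 that follow-up of a barred patient stops at month 13, because the study ends when the last subject "completes either the ETD visit or the active study period and, if eligible, the 12 months on the OLE study". That section defines when the trial ends, not when an individual's follow-up ends; sections 4.3, 4.4 and 6.4 anticipate later contact or testing. What remains is narrower: no 26-month renal assessment is fixed there. Section 4.3 testing is as clinically warranted, footnote 14 is tied to the OLE, and the section 6.4 calls collect vital status only.

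**The population is partly defined.** The endpoint is limited to maintained hematologic responders, and Table 5 provides for that group. But Table 5 reaches OLE entrants only, and section 8.3.2 does not restrict the analysis to them. Patients who stop to start chemotherapy are mostly outside a maintained-response endpoint, so the gap mainly concerns CKD 4/5.

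**The active-period endpoints already capture CKD 4/5.** True, and it limits the damage. They do not supply a 26-month progression rate at the 25% threshold.

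**Counting missing patients only if they had progressed would be no better.** Correct. Assume 30% v 20% true progression, all progressors counted, and 30% of placebo and 10% of NEOD001 non-progressors missing. The rates become 0.30/0.79 = 38.0% and 0.20/0.92 = 21.7%, or 16.2 points instead of 10. Any rule must treat progressors and non-progressors alike.

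**Conclusion.** The point holds as a minor-to-moderate issue for one secondary endpoint. The plan labels the comparison NEOD001 versus placebo, takes its only fixed 26-month data from an all-NEOD001 extension whose entry depends on renal outcome, and has no rule for patients without those data.

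A reader might infer that the bias dilutes a treatment effect. The documents do not support a direction: reversing which arm loses more patients turns 1.4 points into 22.2. Those figures rest wholly on the assumed rates and barred shares. The eGFR overlap needs only the protocol's own thresholds, plus persistence of the fall for baselines below 40.

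Nor does the problem reach the primary analysis or the active-period time-to-event endpoints, which precede the OLE. With about 18% power for a 10-point difference, no significance claim realistically depends on it. The t-test is a separate inconsistency with the synopsis and carries no weight in this conclusion.

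**What to change.** Amend sections 8.1, 8.3.2 and 8.6 and the synopsis, with matching labels in sections 1.1 and 2.

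1. **Population and label.** Analyse by randomised arm in all randomised and treated subjects with a maintained hematologic response at their last hematologic assessment. Describe the result as immediate versus delayed NEOD001, not as a placebo comparison at 26 months.
2. **One rule for every patient without 26-month renal data, progressed or not.**
   - Progression: use all renal assessments from baseline, including any standard-of-care results recorded. Estimate progression by month 26 by Kaplan-Meier per arm with a stratified log-rank test, censoring non-progressors at their last renal assessment.
   - Response: use the last available renal status for all such patients, with an observed-data-only sensitivity analysis. State this as an exception to the no-imputation rule in section 8.6.
3. **Reporting.** Give per arm the numbers with no 26-month renal data, barred from the OLE, declining the OLE, and dead.
4. **Test.** For response, keep only the stratified CMH test and delete the t-test, in line with the synopsis. The synopsis entry for progression changes to the log-rank test.

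**Cost.** Wording only; no new visits. Table 1 already has creatinine at the confirmatory EOS visit and free light chains at the initial EOS/ETD visit.

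**Downsides.** The endpoint can no longer be presented as placebo-controlled. Carrying the last response status forward assumes persistence, and for ETD patients it may rest on an early assessment. Censoring at the last assessment may be informative. Subset membership for patients outside the OLE rests on initial-EOS or ETD hematologic status, because no free light chains are scheduled at the confirmatory visit.

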### 8.3.3 Ancillary Studies Analyses

The ancillary studies analyses will be performed by the Amyloidosis Research Consortium (ARC) in collaboration with Tufts Medical Center and the other RAIN study centers. Original forms will be faxed or reported electronically to the ARC data manager for entry into the RAIN ancillary studies database. The ancillary studies database will be maintained by ARC personnel and be accessed by Tufts and ARC data managers. This database is part of the secure REDCap database that is used for this trial.

SF-36 surveys (Appendix 7) will be scored and recorded in a central REDCap data bank. The SF-36 assesses 8 scales of health status from which a physical component summary (PCS) and a mental component summary (MCS) are derived (User's Manual for the SF-36v2 Health Survey, Second Edition). Summary scores will be standardized so a score of 50 corresponds to the average for the US population. Baseline and follow-up SF-36 scores will be compared for each patient and with population norms using 1-sample t tests. Pearson correlations, t tests, Wilcoxon 2-sample tests, and Mantel-Haenszel tests will be used to describe the associations between various component scales and scores of the SF-36 and clinical and demographic characteristics of these patients. The relationship of improvement or worsening in the PCS or MCS to 12 months of treatment with NEOD001 or placebo, and also to the presence or absence of confirmed renal responses, will be examined using the Mantel-Haenszel test. In order to determine whether the QOL measures reflect contributions that were independent of or equivalent to those made by treatment assignment, presence or absence of confirmed renal responses, or clinical characteristics, stepwise proportional hazards regression with the significance level for entry into and for staying in the model set at 5% will be used to identify clinical and health status factors related to changes in QOL measures from the beginning to the end of treatment.

Renal biopsies will be scored by a predefined set of criteria for the degree and pattern of amyloid involvement and distribution (Appendix 8). The renal pathology group will use established criteria, perform the scoring using a standard operating procedure and record results in a central data bank. Comparisons will be made between the NEOD001 and placebo groups by the CMH test stratified by the pre-randomization stratification factors at alpha of 0.05.

The ARC will seek additional funding to perform microarray and miRNA array profiling of renal biopsy specimens from RAIN patients and to conduct biostatistical analyses of the results in collaboration with the University of Michigan investigators, Tufts Medical Center and the other RAIN study centers.

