#### **3.2.3 Ancillary Studies**

Ancillary studies for this trial are being performed in collaboration with the Amyloidosis Research Consortium (ARC; described in synopsis). ARC will maintain ancillary study data in a REDCap database that the Tufts Neely Center for Clinical Cancer Research will create and oversee. The ancillary studies are being performed by a collaborative of Tufts, the ARC and for the gene expression work the University of Michigan. This work is being conducted under CDA and with IP agreements and carve-outs currently being negotiated. Patients will be assigned alphanumeric characters (absent all personal identifying information) that are linked to the Case

Report Forms maintained in REDCap by the participating centers and the Tufts Neely Center for Clinical Cancer Research.

The ancillary studies are designed in order to determine if there are differences among patients who receive NEOD001 and those who do not, and to define and identify differences among patients who have renal responses and those who do not, and renal progression or not, whether or not those patients receive NEOD001.

- Patient reported outcomes: Patients who receive NEOD001 or have renal responses or renal progression may experience changes in their quality of life. Patient reporting of outcomes is very important to in order to answer whether changes in renal disease status are associated with changes in quality of life. We will obtain SF-36 surveys at study entry and at 3, 6, 9 and 12 month visits and at ETD or initial and confirmatory EOS visit (Appendix 7). Scores will be computed and comparisons made by norm-based scoring (User's Manual for the SF-36v2 Health Survey, Second Edition).

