## 8.3 Analysis of Efficacy Endpoints

### 8.3.1 Primary Efficacy Analysis

This stratified randomized double-blind phase 2b study has as its primary efficacy endpoint confirmed renal response at the confirmatory EOS visit to evaluate 12 months of study treatment. The primary efficacy analysis will test the following hypotheses:

- $H_0$ : The confirmed renal response rate after 12 months of treatment is equal between placebo and NEOD001.
- $H_1$ : The confirmed renal response rate after 12 months of treatment is different between placebo and NEOD001.

The primary efficacy analysis of the confirmed renal response rates after 12 months of treatment with NEOD001 or placebo will be performed with the Mantel-Haenszel (MH) test at the alpha=0.05 (two-sided) level of significance. The analysis will be stratified by the randomization stratification variables. The number and percentage, with associated 95% exact confidence intervals (CI) of subjects in each category of response will be presented by treatment group. The proportional treatment difference with associated exact 95% CI will be presented.

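### The one direct NEOD001-versus-placebo comparison of SF-36 turns PCS and MCS into improved or worsened for a Mantel-Haenszel test, with no cut-off and no baseline adjustment; an analysis on the score scale would use the same data better.

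*Combined protocol and SAP*

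**What the plan says.** PCS and MCS are norm-based scores: "Summary scores will be standardized so a score of 50 corresponds to the average for the US population". Section 3.2.3 gives the collection schedule: "We will obtain SF-36 surveys at study entry and at 3, 6, 9 and 12 month visits". It adds the ETD visit or both EOS visits, and Table 1 agrees.

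Section 8.3.3, repeated in the synopsis, names four kinds of SF-36 analysis:

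- Within patient and against norms: "Baseline and follow-up SF-36 scores will be compared for each patient and with population norms using 1-sample t tests".
- Correlations, t tests, Wilcoxon tests and Mantel-Haenszel tests for "associations between various component scales and scores of the SF-36 and clinical and demographic characteristics of these patients".
- The arm comparison, "The relationship of improvement or worsening in the PCS or MCS to 12 months of treatment with NEOD001 or placebo", which "will be examined using the Mantel-Haenszel test". The same sentence gives the comparison by confirmed renal response to the same test.
- A multivariable model intended to separate the contribution of QOL measures from those "made by treatment assignment, presence or absence of confirmed renal responses, or clinical characteristics, stepwise proportional hazards regression", with 5% levels for entering and staying.

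For the arm comparison, the text states no cut-off for improvement or worsening, no rule for unchanged scores, no strata, no alpha and no follow-up visit. The biopsy-score comparison in the same section states both its strata and its alpha.

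**The concern.** The arm comparison is the only randomized contrast among these analyses, and it is the one for which the scores are reduced to categories. That ignores how far a patient's score moved. It also leaves the entry score out of the comparison, although every patient is due to have one. The reader would get a test result but no adjusted mean difference in PCS or MCS and no confidence interval.

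The other analyses do not fill the gap. The 1-sample t tests do not compare arms. The t, Wilcoxon and correlation analyses concern clinical and demographic characteristics, and randomized arm is neither. The stepwise model has no defined event or time, and treatment may not survive selection.

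Section 3.2.3 says that the ancillary studies are meant to show whether patients given NEOD001 differ from those who are not. In a trial sized for a 30-point difference in renal response, a null result from a weak test of quality of life would be hard to read. The open cut-off also leaves room to choose it after the data are seen.

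**Working it through.** **1. The plan's own figure.** No power is stated for SF-36, so the only figure to reproduce is the primary sample size in section 8.5 (25% against 55%, two-sided 0.05, power 0.80). With pooled rate 0.40, n = [1.96 × √(2 × 0.40 × 0.60) + 0.842 × √(0.25 × 0.75 + 0.55 × 0.45)]² / 0.30² = (1.358 + 0.555)² / 0.09 = 40.7. That gives 41 per arm, and power at 41 is 0.803. With 18% dropout, 50 × 0.82 = 41. The figure reproduces, and I use 41 and 50 per arm below.

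**2. Assumptions.** Scores are normal with equal variances and SD 10 in each arm. The baseline-to-follow-up correlation r is 0.5 to 0.7. The documents give neither value, only the norm of 50. Alpha is two-sided 0.05, borrowed from section 8.3.1 ("will be performed with the Mantel-Haenszel (MH) test at the alpha=0.05 (two-sided) level of significance"), because none is stated for the SF-36 test.

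**3. Information kept by categories, relative to a t test on the change score.**
- Two categories with a proportion p improving: φ(z_p)² / [p(1 − p)]. At p = 0.5 this is 0.3989² / 0.25 = 0.637, a 36% loss. At p = 0.3 the loss is 42%, and at p = 0.2 it is 51%.
- Three ordered categories scored −1, 0, 1, with p in each tail: [2φ(c)]² / (2p). With equal thirds, c = 0.431 and φ(c) = 0.364, giving 0.793, a 21% loss.

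**4. Adding the lack of baseline adjustment.** The change score has variance proportional to 2(1 − r) and ANCOVA to 1 − r². The change score is therefore (1 + r)/2 as efficient as ANCOVA: 0.75, 0.80 and 0.85 at r = 0.5, 0.6 and 0.7. Multiplying by step 3:

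| r | two categories, median cut | loss | three equal categories | loss |
|---|---|---|---|---|
| 0.5 | 0.637 × 0.75 = 0.477 | 52% | 0.793 × 0.75 = 0.595 | 40% |
| 0.6 | 0.637 × 0.80 = 0.509 | 49% | 0.793 × 0.80 = 0.635 | 37% |
| 0.7 | 0.637 × 0.85 = 0.541 | 46% | 0.793 × 0.85 = 0.674 | 33% |

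**5. Power.** The SD of the change is 10√(2(1 − r)) = 10.0, 8.94, 7.75. The ANCOVA residual SD is 10√(1 − r²) = 8.66, 8.00, 7.14. Power for means is Φ(Δ / [SD × √(2/n)] − 1.96). For example, with Δ = 5, r = 0.5 and n = 41: 5 / (8.66 × 0.2209) − 1.96 = 0.65, so power is 0.74. For the two-category test, half of the placebo patients improve, against Φ(Δ / SD of change) on NEOD001 (0.691 in this example, power 0.42).

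| n per arm | Δ | ANCOVA, r = 0.5 / 0.6 / 0.7 | t test on change | two categories |
|---|---|---|---|---|
| 41 | 5 | 0.74 / 0.81 / 0.89 | 0.62 / 0.72 / 0.83 | 0.42 / 0.50 / 0.62 |
| 41 | 3 | 0.35 / 0.40 / 0.48 | 0.27 / 0.33 / 0.42 | 0.19 / 0.22 / 0.28 |
| 50 | 5 | 0.82 / 0.88 / 0.94 | 0.71 / 0.80 / 0.90 | 0.50 / 0.59 / 0.70 |

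Simulating 3,000 to 6,000 trials per setting under the same assumptions agrees within about 2 points. At 41 per arm and 5 points it gives 74-87% for ANCOVA and 44-64% for the Mantel-Haenszel test; at 3 points it gives 34-46% and 21-30%. Taking formula and simulation together, the two-category range at 5 points is 42-64%.

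**The case against.** The strongest defence is that nothing here is invalid. A comparison of improved with worsened patients in a randomized trial controls type I error, and the complaint is one of efficiency. SF-36 is neither primary nor secondary, no power is claimed for it, and no trial decision depends on it. All of that stands, and it limits the weight of the point.

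Two stronger readings are tempting, and the documents do not support them.

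- A reader might infer that the Mantel-Haenszel test is the only SF-36 analysis involving treatment. It is not: treatment assignment is named in the purpose of the stepwise regression, and section 3.2.3 also intends comparisons using norm-based scores. Neither specifies a between-arm estimate, so the gap remains, but the accurate statement is that this is the only direct arm comparison named.
- A reader might infer that the plan discards half the information. That holds for two categories cut near the median, compared with ANCOVA at an assumed correlation of 0.5 to 0.7, and it combines two effects: categorizing and not adjusting for baseline. The text never says that there are only two categories, and a Mantel-Haenszel test can use ordered ones. With three equal categories the loss is 21% against the change score.

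Some loss remains under every categorization examined.

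**Conclusion.** The point holds as an improvement to an ancillary analysis. The direct arm comparison of SF-36 is categorical, unadjusted for baseline and without a stated cut-off, while the data for a baseline-adjusted comparison of scores are already being collected. The likely loss is 21-36% of the information against a t test on change (three equal categories; two categories at the median) and 33-52% against ANCOVA, for correlations of 0.7 to 0.5. A two-category cut far from the median loses more. These figures depend on normal scores and assumed correlations; the power figures also depend on SD 10 and on the primary endpoint's 41 evaluable per arm, since no SF-36 analysis set is stated.

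It should not be read as saying that ANCOVA would find an effect that the planned test misses. At 5 points the contrast is clear, but at 3 points with 41 per arm ANCOVA would also fail more often than not. Nor does the weight that section 3.2.3 puts on patient-reported outcomes settle the matter: that sentence concerns whether changes in renal status go with changes in quality of life, not the arm comparison. The primary analysis and the sample size are unaffected.

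**What to change.** In section 8.3.3 and the matching synopsis text, specify the between-arm SF-36 analysis as an ANCOVA of PCS and of MCS at 12 months, with treatment, baseline score and the two stratification factors (hematologic response and renal stage). Name the visit that counts as 12 months, since SF-36 is due at month 12 and at both EOS visits. A repeated-measures model over months 3 to 12 and EOS with the same terms is an equal alternative. Report the adjusted mean difference with its 95% CI. Keep the improved/worsened table as description, with its cut-off, number of categories and handling of unchanged scores stated in advance.

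The cost is one or two sentences in each place. No new data, visits or patient burden are needed.
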